13.5 Investigator Responsibilities

The Eye Pharma-investigator will promptly review documented adverse events and abnormal test findings to determine (1) if the abnormal test finding should be classified as an adverse event; (2) if there is a reasonable possibility that the adverse event was caused by the investigational product and (3) if the adverse event meets the criteria for a serious adverse event.

If the Eye Pharma-investigator's final determination of causality is "unknown and of questionable relationship to the investigational product" the adverse event will be classified as associated with the use of the investigational product, for reporting purposes.

13.6 Evaluation of Causality

AE Relationship to Study Product

The relationship of an AE to the study drug should be assessed using the following the guidelines in Table 5.

Relationship to Product	Comment
Definitely	Previously known toxicity of the agent; or an event that follows a reasonable temporal sequence from administration of the product; that follows a known or expected response pattern to the suspected product; that is confirmed by stopping or reducing the dosage of the product; and that is not explained by any other reasonable hypothesis.
Probably	An event that follows a reasonable temporal sequence from administration of the product; that follows a known or expected response pattern to the suspected product; that is confirmed by stopping or reducing the dosage of the product; and that is unlikely to be explained by the known characteristics of the subject's clinical state or by other interventions.
Possibly	An event that follows a reasonable temporal sequence from administration of the product; that follows a known or expected response pattern to that suspected product; but that could readily have been produced by a number of other factors.
Unrelated	An event that can be determined with certainty to have no relationship to the study product.

Table 5 - AE Relationship to Study Product

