13 ADVERSE EVENTS REPORTING AND DOCUMENTATION

13.1 Overview

An Adverse Event (AE) is "Any untoward medical occurrence in a patient or clinical investigation patient administered a pharmaceutical product and which does not necessarily have to have a causal relationship with this treatment. An AE can therefore be any unfavorable and unintended sign (including for example an abnormal laboratory finding), symptom, or disease temporally associated with the use of a medicinal product, whether or not considered related to the medicinal product".

This definition includes intercurrent illnesses or injuries, exacerbation of pre-existing conditions, and adverse events occurring as a result of drug withdrawal, abuse, misuse or

overdose. Adverse events observed during all periods of the study are to be recorded, including adverse events occurring during a period without study product intake. This also includes adverse events which are reported within in the screening phase (since the patient has signed Informed Consent Form).

Signs and symptoms considered as lack of efficacy and occurring during the study will not be recorded on the AEs Section of the CRF except on the condition that, in the investigator's opinion, they are caused by any reason different from lack of efficacy of study product or meet the definition of serious AE.

Clinically significant findings at screening (e.g., laboratory findings) are not considered an AE/SAE.

If a clinical significant finding recorded at screening worsens (in terms of severity or frequency) during the study, it must be recorded as an AE/SAE.

Unexpected Adverse Event

An Unexpected Adverse Event is any experience not previously reported (in nature, severity or incidence) in the current package insert for the study product.

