### **12.2** Adverse Events

Adverse event will be coded using the last updated version of the Medical Dictionary for Regulatory Activities (MedDRA) dictionary to give a preferred term (PT) and a system/organ class term (SOC) for each. Adverse events will be tabulated by treatment group. Tables will be included the number of patients who experienced at least one AE, of study product-related AEs (defined as definitely, probably, possibly, or unrelated), of serious AEs, and the number of patients withdrawn due to AE, summarized by treatment arm. Comparisons between treatment arms will be performed using chi-square test.

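### The causality scale in Protocol Table 5 has no level for a plausibly timed event of a new kind, and the 13.5 rule for uncertain causality is not carried into the scale or the related-AE analysis

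*Protocol*

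**What the plan says.** Protocol 13.6 makes Table 5 the instrument for causality: "The relationship of an AE to the study drug should be assessed using the following the guidelines in Table 5". Its four levels are:

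- *Definitely*: "Previously known toxicity of the agent; or an event that follows a reasonable temporal sequence from administration of the product", with further conditions on the second limb, namely "that follows a known or expected response pattern to the suspected product; that is confirmed by stopping or reducing the dosage of the product", and no other reasonable explanation.
- *Probably*: reasonable timing, the same pattern and dechallenge conditions, and other explanations unlikely.
- *Possibly*, the lowest of the related levels: reasonable timing, and an event "that follows a known or expected response pattern to that suspected product; but that could readily have been produced by a number of other factors". The pattern condition therefore applies here too.
- *Unrelated*, the only remaining choice, is reserved for cases beyond doubt: "An event that can be determined with certainty to have no relationship to the study product".

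Protocol 13.5 asks a separate question, whether there is a reasonable possibility that the product caused the event. It adds that a final determination of "unknown and of questionable relationship to the investigational product" is to be classed as associated with the product for reporting purposes. The determination is given to a role that joins the sponsor's name to the word investigator; that role is not defined.

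For the analysis, SAP 12.2 tabulates "study product-related AEs (defined as definitely, probably, possibly, or unrelated", and Protocol 14.5 has the same wording. Both compare arms by chi-square test.

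Protocol 13.1 foresees events of a new kind, judged against the package insert: "An Unexpected Adverse Event is any experience not previously reported (in nature, severity or incidence".

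**The concern.** A causality scale should give every event one place. This one leaves a gap where a new safety signal would first appear: an event that starts at a plausible time after dosing, looks like nothing already attributed to the product, and cannot be dismissed with certainty. Protocol 8.3.1 describes the product as a new formulation, so such events cannot be ruled out.

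A site with such an event must either stretch *possibly* or fall back on *unrelated*, and nothing tells it which. Section 13.5 shows that the sponsor wants uncertain events counted on the cautious side, but no text links that rule to Table 5 or to the tables that will be analysed. With four sites choosing for themselves, the related-AE table may reflect local habit as well as the product. The analysis wording makes this worse, because as written it does not separate related from unrelated events.

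**Working it through.** The plan gives no figure on this point, so the check is logical.

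**Inputs.** The level definitions in Protocol 13.6, the uncertainty rule in 13.5, and the analysis wording in Protocol 14.5 and SAP 12.2.

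**Step 1: coverage of Table 5.** Take events that are not certain to be unrelated. Describe each by four yes/no attributes: plausible timing, established or anticipated pattern, improvement on stopping or reducing (dechallenge), and a ready alternative explanation. That gives 2 × 2 × 2 × 2 = 16 combinations, 8 without a pattern and 8 with one. The conditions within a level are read together.

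| Pattern | Timing | Dechallenge | Ready alternative | Level met |
|---|---|---|---|---|
| No | any | any | any | none (0 of 8) |
| Yes | Yes | Yes | No | definitely / probably (1) |
| Yes | Yes | Yes or No | Yes | possibly (2) |
| Yes | Yes | No | No | none (1) |
| Yes | No | any | any | none (4) |

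With a pattern, 1 + 2 = 3 of 8 combinations fit; without one, 0 of 8 fit. If a previously known toxicity alone is enough for *definitely*, known-toxicity events gain a place. The count for events of a new kind stays at 0 of 8, because such an event is not a known toxicity.

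The fourth row is a smaller gap: established pattern, good timing, no dechallenge and no ready alternative. It also has no level unless the event is a known toxicity.

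**Step 2: does 13.5 fill the gap?** Its rule is triggered by an unknown, questionable relationship. Table 5 cannot return that result, and neither section refers to the other. The rule also stops at reporting purposes and says nothing about the tables.

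**Step 3: what reaches the analysis?** Protocol 14.5 and SAP 12.2 name the four levels and no other. Read literally, *unrelated* sits inside the product-related category, so that category would hold every rated event. If the intended meaning is the first three levels (an assumption), an event of a new kind forced into *unrelated* would leave the related count.

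**Step 4: scale.** Protocol 4.1 plans 30 patients per arm. One patient whose only potentially related event is rated one way rather than the other moves that arm's proportion by 1/30 = 3.3 percentage points. How many such patients there will be is not stated.

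**Step 5: what does not depend on the rating.** Protocol 13.4.1 records all AEs whatever the suspected causality. Section 13.4.2 sends all SAEs to the sponsor within 24 hours, related or not. Section 16.5 has the IRB/IEC told of serious and/or unexpected events with no causality filter. Both analysis sections also tabulate patients with at least one AE of any kind.

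**The case against.** The strongest reply is that Table 5 is offered as guidelines, with a column headed as comment, and that 13.5 has its own test and its own conservative default. On that reading 13.5 is the catch-all and only a cross-reference is missing. This has some force: an investigator may use judgement, and 13.5 does not say that its determination must be a Table 5 level. But 13.6 directs the rating to Table 5, and even a generous reading of 13.5 covers reporting only. The tables would still have no place for the event.

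Three stronger readings are tempting, and the documents do not support them.

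- A reader might infer that an event rated *unrelated* drops out of the related-event counts. As SAP 12.2 is worded it does not, since *unrelated* is listed within them. The loss arises only if that wording is a slip, which is likely but not stated.
- A reader might infer that such events escape safety reporting that turns on being unexpected and related. No rule in the documents uses that filter. Reporting to authorities follows local law, which the documents do not reproduce.
- A reader might infer that every event unexpected under 13.1 is unratable. But 13.1 is defined by the package insert, whereas Table 5 speaks of a pattern that is known or expected, with no tie to the insert. An effect that is foreseeable but not in the insert can be unexpected and still be rated. So can an event that is unexpected only in severity or incidence.

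Two side points carry little weight. The absence of a timing condition on known toxicity in *definitely* depends on how the semicolons are parsed, and the AE definition in 13.1 already refers to temporal association. A rule limiting how the sponsor may alter ratings would be a preference, not something the documents call for.

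**Conclusion.** The point holds in a limited form. Table 5 is not exhaustive: a plausibly timed event with no established or anticipated pattern, and no certainty of non-relationship, meets none of the four levels (0 of 8 combinations). The cautious rule in 13.5 has no matching level and does not reach Protocol 14.5 or SAP 12.2, whose wording also wrongly counts *unrelated* as product-related.

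The damage is confined to relatedness ratings and the chi-square comparison of related AEs. Event capture, SAE reporting to the sponsor, IRB/IEC notification, total AE counts and the efficacy endpoints are untouched. The number of affected events is not given, so the size can be stated only per patient, at 3.3 points of an arm's proportion.

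This rests on reading the conditions within a level cumulatively and on Table 5 being the operative scale, as 13.6 says. The eCRF causality codes are not in the documents, so an unknown option may already exist there. If it does, the scale and the analysis text still need to recognise it.

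**What to change.** 1. **Scale.** In Table 5, either remove the pattern condition from *possibly* or add a level for unknown / not assessable. The two are not equivalent. With the condition removed but the alternative-cause clause kept, 2 of the 8 no-pattern combinations fit (plausible timing with a ready alternative, with or without dechallenge). A new event with no other explanation would still have no level. The added level covers all of them, and the smaller gap as well.
2. **Definition of related.** State in Table 5, Protocol 14.5 and SAP 12.2 that related means *definitely*, *probably*, *possibly* and, if added, unknown, and that *unrelated* is excluded. Cross-refer to 13.5.
3. **Data already collected.** SAP 4.2 describes enrolment as done. Write the rule into SAP 12.2 before unblinding, which SAP 4.3 places after database lock, including how unrated or unassessable events are counted.
4. **Assessor.** Say in 13.5 whether the final determination belongs to the site investigator or the sponsor.

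The cost is a few lines of protocol and SAP text and, if the level is added and not already present, one eCRF code. Any re-rating of events already assessed would add site work and should be done blind. The related-AE count may rise slightly in both arms.

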14 STATISTICAL METHODS AND CONSIDERATIONS

Prior to the analysis of the final study data, a detailed Statistical Analysis Plan (SAP) will be issued, describing all analyses that will be performed. The SAP will contain any

modifications to the analysis plan described below. SAS 9.4 for windows (SAS Institute Inc., Cary, NC, USA) will be used for statistical analysis. A level of statistical significance (alpha) of 5% will be used to evaluate statistically significant differences between the two treatment groups, placebo and active treatment.

14.1 Data Sets Analyzed

All eligible patients who are randomized into the study and receive at least one dose of the study product (the Safety Population) will be included in the safety analysis. All eligible patients who are randomized into the study, receive at least one dose of the study product and have at least a post-randomization endpoint estimate (the Intention-to-Treat Population) will be included in the efficacy analysis.

14.2 Demographic and Baseline Characteristics

The following demographic variables collected at screening will be summarized by treatment group: race, gender, age, height and weight.

14.3 Analysis of Primary Endpoint

The number and intensity of relapses will be assessed through instrumental analysis and physical examination. These endpoints will be assessed from baseline to end of treatment.

Mean and standard deviation will be used to describe the number of relapses per patient. The mean number of relapses per patient will be compared between the treatment groups using Student's t-test. ANOVA will be used to include predictive/confounding variables in the model.

In addition, a generalized linear mixed model (GLMM) with Poisson statistical distribution and with the number of relapses as dependent variable will be used to assess the effects of the treatment on reducing the number of relapses, also including in the model other potentially predicting/confounding variables.

The intensity of relapses will be scored as mild (either trace to 1+ cell OR flare \leq 20), moderate (2+ to 3+ cell OR Flare > 20 and < 100) and severe (4+ cell OR Hypopyon OR flare \geq 100). For each patient, the average intensity will be estimated as the mean of the intensity observed during each relapse. The average and the maximum intensity will be compared between treatment groups using Student's t-test. ANOVA will be used to include predictive/confounding variables in the model.

The mean number of relapses per patient observed during the study will be compared to the mean number of relapses reported the previous year within each treatment group using paired t-test or ANOVA, to eventually adjust for predictive/confounding variables. As group means can be somewhat deceptive with small number of events, the patients will be classified based on the number of relapses before treatment and then on the number of relapses after treatment. The number of patients that change class before and after treatment (for example, from a high number of relapses to a low number) will be described and compared between treatment groups.

The primary efficacy endpoints will be analyzed in the following hierarchical order: first, "the mean number and intensity of relapses during the study between treatment groups" and then "the reduction of mean number of relapses between the year before treatment and the study period".

The level of cell damage and inflammation will be assessed through Laser Flare Meter. The difference between treatment groups will be compared using ANCOVA, with the baseline level included in the model.

An analysis of the number of relapses per eye will be also considered, if appropriate.

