3 STUDY OBJECTIVES

3.1 **Primary Objective**

To explore the efficacy of NORFLO[®] ORO in RAU, measured as a long-term reduction of the frequency and severity of relapses, in patients with HLA-B27-associated uveitis, under conditions of routine medical practice. The reduction of the mean number of relapses per patient between the year before study treatment and the study period will also be assessed.

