14.7 Sample Size

In a previous study²⁵, 275 relapses on 106 patients were observed, corresponding to a mean number of relapses per patient of 2.6 (Standard deviation, SD: 0.7) while in the post-treatment group 36 relapses were registered corresponding to a mean number of relapses per patient of 0.34 relapses/patient. With a statistical power of 80% and a significance level (alpha) of 5% and a common SD of 0.7, 46 patients are needed to observe a difference of 0.6 relapses/patients between the two treatment groups (i.e., 2 relapses/patient in the NORFLO[®] ORO treatment group vs. 2.6 in the placebo treatment group). To take into account a potential dropout rate of 20% over 12 months, 60 patients will be recruited. Subjects dropping out the study because they are beginning systemic therapy with anti-inflammatory, immunosuppressive, biologic drugs will be replaced.

A second primary endpoint, i.e. the reduction of mean number of relapses between the year before treatment and the study period, will be examined. No formal sample size estimate is feasible on this endpoint, as it was not tested previously and no reasonable scenario can be drawn.

As the two endpoints will be assessed in a hierarchical order (first, "the mean number and intensity of relapses during the study between treatment groups" and then "the reduction of mean number of relapses between the year before treatment and the study period"), according to the "Points to consider on multiplicity issues in clinical trials", issued by the Committee for Proprietary Medicinal Products (CPMP - 2002), no sample size adjustment for multiplicity is needed.

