### 5. STUDY ENDPOINTS

### 5.1 Primary Endpoints

The primary efficacy endpoint is the mean number and intensity of relapses per patient occurred during the study, from baseline to end of treatment, in patients treated with the NORFLO® ORO compared to patients treated with placebo.

The reduction in relapses was determined by a reduction of the intraocular inflammation through a clinical and diagnostic evaluation that includes Laser measurement of AC flare with Kowa LFM 600 or LFM 700 (Normal range 2.5-7 ph/ms, Outside normal range > 10 ph/ms).

The reduction of the mean number of relapses per patient between the year before treatment and the study period within each treatment group will also be assessed.

The reduction of cell damage and inflammation were measured by the Laser Flare Meter, in patients affected by HLA-B27-associated uveitis after treatment with NORFLO® ORO, when compared to placebo.

The number and intensity of relapses and LFM data, used in primary efficacy endpoints, were reported in the first unscheduled visit.

Only patients with relapses will be analyzed in primary efficacy endpoints.

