## 11.4 Efficacy Analysis

## 11.4.1 Primary Efficacy Endpoints

The number and intensity of relapses were assessed through instrumental analysis and physical examination. These endpoints will be assessed from baseline to end of treatment.

When a relapse occurs, the data reported in the first unscheduled visit concerning the intensity of the relapse and data from LFM will be used as they are taken before the administration of both systemic and topical cortisone.

Mean and standard deviation will be used to describe the number of relapses per patient. The mean number of relapses per patient will be compared between the treatment groups using Student's t-test. ANOVA will be used to include predictive/confounding variables in the model.

In addition, a generalized linear mixed model (GLMM) with Poisson statistical distribution and with the number of relapses as dependent variable will be used to assess the effects of the treatment on reducing the number of relapses, also including in the model other potentially predicting/confounding variables.

The intensity of each relapse will be scored as mild (either trace to 1+ cell OR flare  $\leq 20$ ), moderate (2+ to 3+ cell OR Flare  $\geq 20$  and  $\leq 100$ ) and severe (4+ cell OR Hypopyon OR flare  $\geq 100$ ). For each patient, the average intensity will be estimated as the mean of the intensity of relapses observed during the study. The average and the maximum intensity will be compared between treatment groups using Student's t-test. ANOVA will be used to include predictive/confounding variables in the model. As this variable could likely be not normally distributed, Wilcoxon Mann-Whitney will be also used.

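### Average relapse intensity is a mean over the relapses that still occur, so selective prevention of milder attacks raises it and the step 1 severity comparison can point to harm when no patient is worse off

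*Protocol*

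**What the plan says.** The primary objective (Protocol 3.1) is efficacy "measured as a long-term reduction of the frequency and severity of relapses". Protocol 14.3 grades each relapse as mild, moderate or severe from cells, hypopyon or flare. It then forms a per-patient mean: "For each patient, the average intensity will be estimated as the mean of the intensity observed during each relapse". SAP 11.4.1 keeps the same denominator: "For each patient, the average intensity will be estimated as the mean of the intensity of relapses observed during the study".

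On the test, Protocol 14.3 says: "The average and the maximum intensity will be compared between treatment groups using Student's t-test". SAP 11.4.1 adds a Wilcoxon Mann-Whitney test. Both intensity variables sit with the relapse count at the first step of the hierarchy, described as "the mean number and intensity of relapses during the study between treatment groups".

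Neither document assigns numeric values to the three grades, gives an expected severity mix, defines a severity total per patient, or says how to read a favourable count beside an unfavourable intensity.

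**The concern.** The product is supposed to change the denominator of its own severity measure. A patient whose relapses would have scored 1, 1 and 3 averages 5/3 = 1.67. If both mild attacks are prevented, the average is 3.0. That patient has had two attacks fewer and none worse, yet the variable has almost doubled.

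This composition effect occurs within patients who still relapse, so it does not depend on which analysis population is chosen. At stake is the severity half of the primary objective. The trial could report fewer but more severe relapses when severe relapses per patient are the same in both arms.

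**Working it through.** **Inputs from the documents.** Protocol 14.7 gives 2.6 versus 2.0 relapses per patient, SD 0.7, alpha 5%, power 80%, and 60 recruited with 20% dropout. The number analysed per arm is 60 × 0.8 / 2 = 24.

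**Assumptions.** Two-sided testing; scores mild = 1, moderate = 2, severe = 3; the severity mixes; and which classes the product prevents. None of these is in the documents.

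**The plan's own figure.** n per arm = 2(1.96 + 0.84)² × 0.7² / 0.6² = 21.3, so 22 per arm or 44 in total. With the exact t distribution, power is 79.3% at 22 and 81.1% at 23 per arm, which gives the stated 46. Dropout: 46 / 0.8 = 57.5, so 58; the plan recruits 60. The figure reproduces, but it sizes the relapse count only, not intensity.

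**Expected averages.** Average = (1 × mild + 2 × moderate + 3 × severe) / relapses, using expected relapses per patient.

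- (a) Mix 30/40/30%, only mild attacks prevented. Placebo 0.78, 1.04, 0.78: 5.20 / 2.6 = 2.00. Product 0.18, 1.04, 0.78: 4.60 / 2.0 = 2.30.
- (b) Same mix, half the prevented attacks mild and half moderate. Product 0.48, 0.74, 0.78: 4.30 / 2.0 = 2.15, against 2.00.
- (c) Assumed mix 1/40/59%, moderate attacks prevented. Placebo 0.026, 1.04, 1.534: 6.708 / 2.6 = 2.58. Product 0.026, 0.44, 1.534: 5.508 / 2.0 = 2.75. The mix comes from the flare study of 44 patients in Protocol section 2 (mean 160 ± 22 ph/ms), reading ± 22 as a standard error and assuming a lognormal shape.

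Expected severe relapses per patient before any withdrawal are equal between arms in all three (0.78, 0.78, 1.534). The severity total falls on product in all three: by 0.60, 0.90 and 1.20.

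**Simulation.** 24 per arm, placebo counts rounded Normal(2.6, 0.7), t-test on average intensity among patients who relapse. The second column ends follow-up at the first severe relapse. That approximates Protocol 7.1 (flare above 100 ph/ms) and 10.4 (systemic treatment), both of which withdraw the patient.

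| Scenario | Significantly worse, full follow-up | Ending at first severe relapse |
|---|---|---|
| (a) | about 53% | about 26% |
| (b) | about 15% | about 8% |
| (c) | about 39% | about 22% |
| Proportional prevention | about 2-3% | near nominal |
| (a), and 30% of remaining attacks drop one class | about 4% | about 2% |

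Repeat runs of (a) to (c) differed by up to about 4 percentage points. Poisson counts with full follow-up give 47%, 14% and 35%. Another assumed mix, 50/35/15% with only mild attacks prevented, gives 24-26%, and 13% when follow-up ends at the first severe relapse.

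**Does anything planned remove the effect?** The Wilcoxon test changes the test and leaves the denominator as it is. Maximum intensity is much less affected (significantly worse in 2-6% of trials in (a) to (c)) but does not correct the average. Giving relapse-free patients a 0 while keeping the per-patient mean still leaves 5-23% significantly worse at the planned effect from 2.6 relapses, under mixes 50/35/15% and 35/40/25%.

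**The severity-weighted count.** With relapse-free patients at 0, it is significantly worse in under 1% of trials. It has limits. Under proportional prevention with no change in severity per attack it is significantly better in about 54%, because it largely re-tests the relapse number. Under pure attenuation with no change in number it finds benefit in about 16% of trials, against 30% for the average.

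**The case against.** The strongest reply is that the average answers a legitimate question, how severe an attack is when it happens, and in scenario (a) the remaining attacks really are more severe on average. The relapse count stands beside it at the same step and moves the right way, and the maximum barely moves. Nothing in the documents says that the product spares severe attacks. Protocol section 2 and the objective in 3.1 expect fewer and milder relapses, and with modest attenuation the false signal all but disappears. The withdrawal rules roughly halve the full follow-up rates. They also sit badly with scenario (c), where observed placebo relapses would fall to about 1.5 per patient instead of 2.6.

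Much of this stands: the effect is conditional, the full follow-up rates are upper figures for their scenarios, and (c) is the weakest of the three. What does not stand is that the other variables settle the matter, because no rule says how the count, average and maximum are read together when they disagree.

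A reader might go further and infer that an effective product will probably be shown as harmful, or that the average should be dropped. The documents support neither. They give no severity mix and no evidence of selective prevention, and the average is the more sensitive of the two measures to attenuation per attack.

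**Conclusion.** The point holds as a conditional weakness. A per-patient mean over the remaining relapses rises when milder attacks are selectively prevented, and the plan tests it at step 1 with no safeguard. Where prevention is selective and the remaining attacks are not attenuated, the chance of a significant result in the wrong direction is about 8% to 26% in the three scenarios with follow-up ending at the first severe relapse, and about 15% to 53% with full follow-up. It is 2-4% under proportional prevention or with modest attenuation.

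The direction of the effect is arithmetic. Its size rests on the assumed scores, mixes and selectivity. Ending follow-up at the first severe relapse slightly overstates withdrawal, since 4+ cells or hypopyon with lower flare need not trigger it.

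A reader might also count the SAP 5.1 rule, "Only patients with relapses will be analyzed in primary efficacy endpoints", as part of this defect. It is a separate point: lifting it would leave the composition effect among relapsers in place, so it is not counted here.

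**What to change.** In Protocol 14.3 and SAP 11.4.1 and 11.5, before the blind is broken:

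1. State the numeric scores for the three grades.
2. Add, for all ITT patients with 0 for no relapse, a severity-weighted relapse count per patient (sum of the scores) and the numbers of mild, moderate and severe relapses per patient by arm. Use the same model and follow-up handling as for the relapse number, and say that the relapsers-only rule does not apply to these measures.
3. Keep average and maximum intensity, labelled as conditional on having relapsed.
4. State that a higher average does not count as worsening unless the all-patient severity measures also worsen.

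The cost is some wording, a few derived variables and one table. No new data are needed, and SAP section 13 is the place to record the change. The downside is that the weighted count overlaps with the relapse number and is less sensitive to pure attenuation (about 16% against 30% at 24 per arm). It therefore supplements the average, and the table by class shows where any difference lies.
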